### **4.2. Specific Objectives**

1. To assess the level of knowledge and practice of Health care professional about Enhanced recovery after surgery program.
2. To determine the frequency of postoperative adverse events and complications after laparoscopic cholecystectomy (tress, fatigue, nausea and vomiting)
3. To determine the average length of hospital stay and bed turn over after laparoscopic cholecystectomy
4. To determine the rate and reason of overnight and re-admissions
5. To assess the patients' acceptance of ERAS program and the overall satisfaction
6. To determine the patient cost benefit when ERAS is implemented correctly.

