### **5.2.5. Postoperative care**

- Analgesia: IV Paracetamol or Katamine administration when necessary.
- No opioids
- Treatment of Nausea and vomiting when necessary

- Pain assessment every 4 hours using pain NRS scale by nursing staff
- If pain not severe: Paracetamol + Ibuprofen or Diclofenac
- Re-feeding
  - Two to 4H after surgery: Liquid diet and mobilization.
  - Withdrawal of intravenous infusions (0.7–1 ml/ kg/h) was obtained during
  - From 8H: light semiliquid meal
  - From the 12H after surgery: a free diet and patient mobilization was further encouraged and increased gradually. All the meals had to be consumed sitting at the table.
- From 24h after surgery: Blood works (FBC and CRP) and Discharge

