#### **5.2.6. Discharge & Post discharge**

The important criteria for the patient's discharge from the hospital are: Normal vital signs and blood works, absence of complications or symptoms, a digestive function enabling the patient to eat without nausea or vomiting, return of intestinal transit with emission of gas (stool not required), autonomy to move and post-operative pain relief with oral analgesics (2).

After the discharge for all the patients, the surgeon will make follow up on phone on day 3, 5 day and day 7 to detect any signs of complications during the first week. If no complaints the out patient clinic evaluation will be planned at 15 and 30 days from the operation. The patient will be given oral analgesia for at least 48 hours.

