Continuous variables were presented as mean  $\pm$  standard deviation or median (range) when appropriate and categorical variables will be presented as frequency (percentage). A Univariate analysis will be performed through a stepwise linear regression model using length of hospital stay as dependent variable and age, BMI, gender, ASA score, intraoperative infusions, pain, analgesia, nausea, vomiting, 30 days-readmission rates, presence of complications and mortality as independent factors. Variables with significant link will be crossed with outcome variables to draw their correlation overnight, using Multivariate logistic regression A p value  $< 0.05$  will be considered statistically significant.

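### The length-of-stay regression lists 30-day readmission, which can only follow the stay, among 12 stepwise candidates, and leaves open whether complications found after discharge count

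*Protocol*

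**What the plan says.** Protocol section 5.3 sets out the analysis of LOS in two sentences. The first reads: "A Univariate analysis will be performed through a stepwise linear regression model using length of hospital stay as dependent variable". The candidates that follow number 12. They are four patient characteristics (age, gender, BMI, ASA), intra-operative infusions, four postoperative items (pain, analgesia, nausea, vomiting) and, at the end, "30 days-readmission rates, presence of complications and mortality as independent factors". The second sentence reads: "Variables with significant link will be crossed with outcome variables to draw their correlation overnight, using Multivariate logistic regression". Significance is set at p below 0.05.

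Other sections bear on the candidates:

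- Section 4.2 makes readmission an objective in its own right: "To determine the rate and reason of overnight and re-admissions". Section 6 gives it a results table (Table 7).
- Section 5.2.6 makes discharge depend on "absence of complications or symptoms, a digestive function enabling the patient to eat without nausea or vomiting". It then provides phone calls after discharge "to detect any signs of complications during the first week", with clinic visits at 15 and 30 days.
- Section 5.1 gives a sample of 50 to 70, and section 5.3 recruits until at least 50.
- Section 2 puts the complication rate in current practice at about 5%.

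**The concern.** A predictor of LOS has to exist before the stay ends. Readmission does not: a patient must be discharged first. If LOS were read as total days including a readmission, the variable would be part of its own outcome, so the problem remains on either reading. Section 7 asks whether one-day discharge is safe, which makes readmission a possible consequence of the stay. In a model with several terms, adjusting for a consequence of the outcome also distorts the other coefficients.

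Complications are a mixed case. One that occurs in hospital can prolong the stay under the discharge criteria. One first found by phone or in clinic cannot. The variable as listed does not separate them.

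The selection procedure adds a second problem. Stepwise regression reports p-values as if the chosen variables had been named in advance, and here the chosen variables then pass to a logistic model on the same patients. The text calls the stepwise model univariate, which it is not, and the logistic model's outcome cannot be identified from its sentence.

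At stake is the comparative LOS table (Table 9 in section 6). It could present readmission, or a complication found after discharge, as a factor associated with a stay that was already over.

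**Working it through.** **Order of events.** Three of the candidates, set against the end of the index stay:

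- 30-day readmission: always after it.
- Complications: before it (and then a discharge criterion, section 5.2.6) or after it (found at follow-up, same section).
- Mortality: before or after it. The Protocol gives no expected rate. With emergencies and ASA IV excluded, few or no deaths are likely in 50 to 70 patients, and a variable that is zero for everyone drops out of the model.

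This part needs no arithmetic. The Protocol gives no expected readmission rate, so no numerical size can be put on the readmission error itself.

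**The plan's own figure.** Section 5.1 uses a proportion of 5%, a margin of ±5%, 95% confidence and a population of 1,600. Then n0 = 1.96² × 0.05 × 0.95 / 0.05² = 73.0. With the finite-population correction, 73.0 / (1 + 72.0/1600) = 69.8, rounded up to 70. This reproduces the upper end of the stated range; 50 patients give about ±6%. The calculation concerns the precision of one proportion and says nothing about how many predictors a regression can carry.

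**Patients per candidate.** 50/12 = 4.2 and 70/12 = 5.8.

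**False selection.** Section 5.3 states no entry level, so 0.05 is assumed. For k independent candidates unrelated to LOS, the chance that at least one is selected is 1 − 0.95^k:

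- k = 12 (nothing related): 1 − 0.95^12 = 46%.
- k = 7: 1 − 0.95^7 = 30%. Here the five candidates that section 5.2.6 ties to discharge (complications, nausea, vomiting, pain, analgesia) are truly related.
- k = 6 (the same, with no deaths): 1 − 0.95^6 = 26%.

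A simulation of stepwise selection (entry 0.05 and removal 0.10, both assumed; 12 independent noise variables; 1,500 data sets per sample size) gave 46.5% at n = 50 and 47.3% at n = 70, in line with the formula. When something was selected, the noise model appeared to explain on average 15% (n = 50) or 11% (n = 70) of the variance in LOS.

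**Does removing the outcomes suffice?** Without readmission, 11 candidates remain: 1 − 0.95^11 = 43%. Without mortality as well, 10 remain: 1 − 0.95^10 = 40%. The selection problem is therefore separate and needs its own correction.

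**Complications.** At 5%, 50 × 0.05 = 2.5 and 70 × 0.05 = 3.5 events are expected. The binomial chance of two or fewer is 54% with 50 patients and 31% with 70. A complication term would rest on very few patients, fewer still once those after discharge are set aside.

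**The case against.** The strongest reply is that section 5.3 also states the aim more loosely, as finding variables associated with LOS in a univariate analysis. If each variable is tested alone, the p-value linking LOS and readmission is the same whichever is called dependent, and whether early discharge goes with readmission is a fair question. On that reading the error is largely one of labelling. This stands as far as it goes. But the text specifies a stepwise model with readmission as an independent factor, and there the direction does matter.

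It can also be said that variable windows belong in a SAP or on the data checklist, neither of which is shown. That is right for pain, analgesia, nausea and vomiting. A reader might infer from "Pain assessment every 4 hours using pain NRS scale by nursing staff" that recorded pain must rise with LOS simply because longer stays have more checks. The Protocol does not support this: it does not say how pain will be coded for the model, and a single score or a fixed early window would remove the effect. For complications a SAP could likewise restrict the variable. The point is limited to this: the list as written admits events after discharge.

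A reader might infer that 46% is this study's false-positive rate. It is not. It assumes that nothing is related to LOS, which the discharge criteria make unlikely. Prespecification does not abolish chance findings either: with five independent null terms, 1 − 0.95^5 = 23% of studies would still show at least one.

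Nor do the documents support keeping in-hospital complications out of the model on principle, since their absence is a discharge criterion.

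Finally, a reader might take the logistic outcome to be an overnight stay, which would hardly vary given "From 24h after surgery: Blood works (FBC and CRP) and Discharge". The sentence is too unclear to say that this is the outcome; it shows only that the outcome must be named.

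**Conclusion.** The point holds, for a secondary analysis. Placing 30-day readmission among the predictors of LOS is wrong as stated and rests on no assumption. Mortality belongs with the outcomes for a similar reason and matters little in practice. The complication variable needs a cut at index discharge. Stepwise selection from 12 candidates in 50 to 70 patients gives p-values that cannot be taken at face value. The chance of at least one false factor is at most about 46%, and 26% to 30% in the more plausible case, assuming independent candidates and entry at 0.05.

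A reader might infer that the study's LOS result is compromised. It is not. The average LOS (specific objective 3, Table 5) does not depend on this model, and no specific objective asks for predictors of LOS. The effect is confined to Table 9 and the logistic model that follows from the selection. The correction should be made, since section 7 promises recommendations to other hospitals and Table 9 could be used to support them.

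**What to change.** 1. Remove 30-day readmission and mortality from the LOS predictors and report them as outcomes. If the link with early discharge is of interest, show readmission by LOS descriptively.
2. In any LOS analysis, count only complications that occurred before index discharge. With so few expected, present this mainly as a description.
3. Replace stepwise selection with one short model fixed in advance from the section 5.3 variables that are known before discharge. Call it multivariable and exploratory, and report coefficients with 95% confidence intervals. The exact number of terms is the study team's choice; it should be small for 50 to 70 patients.
4. Drop the logistic model fed by the selection. If one is kept, name its binary outcome (for example, a stay beyond the 36 hours in section 3) and fix its few variables in advance.

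The cost is analysis wording and one checklist field, recording whether each complication came before or after index discharge. No extra patients and no change to care are needed. The drawback is that Table 9 will show fewer significant factors. The gain is less in the count of chance findings than in estimates and intervals not distorted by selection, and in a table free of predictors that arise after the stay.

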## **6. Expected Results**

Table 1: Level of awareness and knowledge of ERAS among perioperative care health professionals

Table 2: Baseline characteristics of patients

Table 2: Acceptance rate of patients in ERP

Table 3: Rate of adverse events (Stress, fatigue, pain, nausea and Vomiting)

Table 4: Complications of laparoscopic cholecystectomy

Table 5: The average length of hospital stay

Tableau 6: Cost of laparoscopic cholecystectomy

Table 7: Rate of overnight and readmission

Table 8: Overall satisfaction of patients after laparoscopic cholecystectomy in ERP

Table 9: Comparative analysis of length and independents variables

## **7. Significance of the study**

The results from this study will determine if ERP can be implemented in our settings and laparoscopic cholecystectomy patients are safe to be discharged on one-day post-operative period in a teaching hospital in Rwanda to increase bed turnover and decrease patients hospital costs.

Recommendations will be formulated to encourage surgeons and hospitals in Rwanda to put in place the ERAS protocols and test it for other surgeries. Finally, this study may posit a direction for related future researches

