## **2. Problem statement**

All surgeries, including laparoscopic surgery, represent a major stressor to the patient with possible sequelae for post-operative well being, including decline in functional capacity, cognitive ability, and even cancer spread. Comorbidities such as diabetes, ischemic heart and vascular disease, stroke, and others have a larger impact on postoperative morbidity and mortality than age (21) (10).

ERAS pathways have been successfully implemented in many surgical specialties, including gastrointestinal, hepato-biliary, pancreatic, urologic, gynecologic, and urologic surgery (22) (23) (24).

The strongest evidence so far has been described in patients undergoing open colorectal procedures (6) (25) (26). Combining minimally invasive laparoscopic surgery and ERAS has been shown to have important clinical and economic benefits and significant reductions in length of hospital stay, but its spread remains slow worldwide.

Implementation of ERAS pathways improves clinical outcomes and induces substantial economic gains (15) (16) (2), and is becoming the optimal strategy for many surgeries when technically feasible (27) (28) (10).

Laparoscopic cholecystectomy can be performed as a day-case procedure with a low rate of complications and admissions/readmissions. Patient acceptance in terms of quality of life variables is similar to that for cholecystectomy with an overnight stay. The day care strategy is associated with a reduction in cost (29).

Laparoscopic cholecystectomy in ERAS program should optimize the surgical outcome and improve a quick recovery and decrease the length of hospital stay. At the University Teaching of Kigali, the current practice is to admit patients for laparoscopic cholecystectomy 24 hours prior to surgery and to discharge most patients within two to three days of surgery with a rate of complications around 5%.

Patients overcrowd CHUK and the hospital bed management is a serious challenge. Patients coming far from their homes and with limited financial resources are suffering to get admitted in hospital for elective and none urgent surgeries like cholecystectomy, We believe that ERP can benefit the hospital with a rapid bed turnover rate, and reduces cost for surgery and hospitalization while providing to the patients with quality care and the same time increasing the comfort of the patient in the post-operative period and minimizing the postoperative complications.

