## **5. Research Methodology**

### **5.1. Methods and Settings**

This is a prospective and cross sectional study. The study will be conducted in Rwanda at the University Teaching Hospital of Kigali from January to December 2021.

Rwanda is a country of 11.9 million in East Africa. There are approximately 80,000 surgical procedures performed annually in Rwanda, 510 major operations per 100,000 populations (30). Rwanda has 4 main referral hospitals performing surgical operations including laparoscopic procedures. The referral hospitals include: University Teaching Hospital (CHUK), University Teaching Hospital of Butare (CHUB), Rwanda Military Hospital (RMH) and King Faisal Hospital, Kigali (KFH, K)

The University Teaching Hospital of Kigali (CHUK) is the major public, tertiary referral and teaching hospital in Rwanda and it is located in the capital in Kigali. It has 565 beds and 11 operating theaters shared among all surgical services. It provides approximately up to 1600 major operative cases in general surgical services every year including 140 cases of laparoscopic surgeries with 75 cases of laparoscopic cholecystectomies. The CHUK started performing laparoscopic surgery routinely long time before others and currently it performs more than 60% of laparoscopic surgeries performed in the Country in different specialties including general surgery, Urology and Gynecology. Considering the above reason, we selected this hospital to represent others and be the site of our research interest.

This study will be conducted in general surgical unit at the University Teaching Hospital of Kigali (CHUK), it has a capacity of 2 operating rooms with 2 lap towers with complete sets of laparoscopic material and around 40 in patient beds.

The population proportion of laparoscopic cholecystectomy is 5% within a total general surgical population size of 1600 patients per year. A range of 50 to 70 patients will allow to have a confidence level of 95% that the real value is within  $\pm 5\%$  of the measured value and have relevant conclusions.

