#### **5.3. Data collection and analysis**

A baseline survey will be conducted to assess the awareness and knowledge of health care professional in charge of perioperative care. From November 2021, we will put in place an ERAS protocol for laparoscopic cholecystectomies. Patients living in Kigali and near Kigali having an easy communication means will be sensitized to adhere to the program.

A multidisciplinary team (Surgeons, Anesthesiologists, nurses, anesthetists and psychologists) will be mobilized to participate in the team. A google sheet questionnaire will be designed to collect information about the awareness and knowledge of perioperative health care professional about ERAS programme and then

a modified ERAS protocol will be put in place and data collection will be done using a coded checklist form and consecutive selection of patients will be done during the study period until we reach at least 50 patients. The operative procedures and instrumentation will be standardized for laparoscopic cholecystectomy, and surgeons who will perform the procedures will be having expertise in laparoscopic cholecystectomy. Reasons for conversion from laparoscopic to open cholecystectomy will be recorded and documented. Emergency patients and patients defined as ASA IV and pediatric patients aged below 16 years will be excluded.

Data will be collected for age, gender, indications for surgery, American Society of Anesthesiology (ASA) class, operative time, adverse events (pain, nausea and vomiting), length of hospitalization, and intra- and post-operative complications. The expenses of surgery and in-hospital care will be calculated and analyzed. On discharge, on day 3 of discharge, day 10, day 15 and day 30 of discharge patient will report outcomes and will be recorded by Surgical Recovery Scale. After discharge, the patients will be called or texted on phone to know about their status and collect information. Data will be recorded using EXCEL. Statistical analysis will be done using SPSS software and the one-way analysis of variance (ANOVA) test, the Chi-square test, and the t Student's test will be used when appropriate for comparisons.

A Univariate analysis will be done to determine variables associated with the length of hospital stay. Pearson's chi square will be calculated to compare variables and..

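### Fifty patients miss the stated 5-point precision at a 5% complication rate, and 50 to 70 patients cannot carry the promised determination that one-day discharge is safe

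*Protocol*

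**What the plan says.** - **Safety claim.** Section 7 (Significance of the study) says the results will determine whether the programme can be implemented and whether "laparoscopic cholecystectomy patients are safe to be discharged on one-day post-operative period". Recommendations to surgeons and hospitals in Rwanda are to follow.
- **Current rate.** Section 2 (Problem statement) describes present practice as to "discharge most patients within two to three days of surgery with a rate of complications around 5" per cent. The figure is approximate and has no denominator.
- **Precision.** Section 5.1 (Methods and Settings) states: "A range of 50 to 70 patients will allow to have a confidence level of 95% that the real value is within" plus or minus 5% "of the measured value and have relevant conclusions". The 5% proportion used there is the share of cholecystectomies among 1600 general surgical patients a year, not a complication rate.
- **Minimum size.** Section 5.3 (Data collection and analysis) says "consecutive selection of patients will be done during the study period until we reach at least 50 patients".
- **Safety objective.** Section 4.2, objective 2, is descriptive: the frequency of adverse events and complications. No safety threshold or margin is given anywhere.

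**The concern.** The protocol promises two things of a sample that may stop at 50: a precision of 5 points and a determination of safety. For a complication rate near the only figure the protocol gives, the first is not met at 50. The second asks more than 50 to 70 patients can deliver.

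At stake is how an unremarkable result would be used. Two or three complications in 50 (4% or 6%) look like the current 5%. If that resemblance were taken as proof of safety, recommendations to other hospitals would rest on data that are also compatible with a rate twice as high.

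**Working it through.** **Inputs.** n = 50 (minimum, section 5.3) and n = 70 (upper end, section 5.1); rate p = 0.05 (section 2); 95% confidence, read as two-sided because of the plus-or-minus form; d = 0.05, read as percentage points; N = 1600 (section 5.1). The doubled rate of 10% is an illustration, not a protocol figure.

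**1. The protocol's own figure.** The usual formula for one proportion is n0 = 1.96² × p(1 − p) / d².
- n0 = 3.8416 × 0.05 × 0.95 / 0.0025 = 73.0.
- With the finite-population correction, n0 / (1 + (n0 − 1)/N) = 73.0 / (1 + 72.0/1600) = 69.8, or 70.

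The upper end of the range is therefore reproduced. The lower end of 50 is not.

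**2. Half-width at a 5% rate.** Half-width = 1.96 × √(0.05 × 0.95 / n).
- n = 50: 1.96 × √0.00095 = 6.0 points (5.9 with the correction for N = 1600).
- n = 70: 1.96 × √0.000679 = 5.1 points (4.99 with the correction).

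**3. Exact (Clopper-Pearson) two-sided 95% limits.** For zero events the upper limit is 1 − 0.025^(1/n); for n = 50 this is 1 − 0.025^(0.02) = 7.1%.

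| Complications | Lower | Upper |
|---|---|---|
| 0/50 | 0% | 7.1% |
| 1/50 | 0.05% | 10.6% |
| 2/50 | 0.5% | 13.7% |
| 3/50 | 1.3% | 16.5% |
| 0/70 | 0% | 5.1% |
| 2/70 | 0.3% | 9.9% |
| 3/70 | 0.9% | 12.0% |

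With 50 patients, a rate of 10% is excluded only if there are no complications at all. Both results nearest the current rate (2/50 and 3/50) leave 10% inside the interval.

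**4. Power to detect a rise from 5% to 10%, n = 50, exact one-sample binomial.**
- One-sided 2.5%: reject at 7 or more events (P = 0.012 at 5%). Power = P(X ≥ 7 at 10%) = 0.230.
- One-sided 5%: reject at 6 or more events (P = 0.038 at 5%). Power = P(X ≥ 6 at 10%) = 0.384.

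**5. How often a doubled rate would look unremarkable.** If the true rate were 10%, the chance of 3 or fewer complications in 50 is 0.25.

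**The case against.** Several points on the other side stand, and they limit what can be claimed.

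- **No result could show a rate below 5%.** A reader might infer this from the zero-event limits. It holds for two-sided exact intervals but not in general. The protocol does not state the sidedness of its p < 0.05. With a one-sided 95% exact bound, 1 − 0.05^(1/n), zero events gives 4.95% at n = 59 and 4.19% at n = 70, both below 5%. At n = 50 the same bound is 5.8%.
- **Safe means below 5%.** The protocol never says so. The 5% is background, and earlier discharge need not lower complications to be acceptable. A looser criterion could be met: an illustrative 10% limit is excluded by 0/50 and by 2/70.
- **A tripling is left open.** This is true of 3/50 (16.5%) but not of 2/50 (13.7%), so only the doubling is claimed here.
- **The whole range misses the stated precision.** It does not. At 70 patients the half-width is essentially 5 points.
- **The 5% in section 5.1 is a different quantity.** This is correct. But the sentence promises precision for the measured value and useful conclusions, and complications are among the values to be measured.
- **Section 7 is aspirational, and no text says how two or three events would be read.** The misreading is a risk, not a stated plan. Even so, the section promises a determination where objective 2 only describes a frequency.
- **Interval methods can wait for the analysis plan.** Their absence is not the criticism. The criticism is of what the protocol asserts.

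**Conclusion.** The point holds in a limited form: the text is wrong as written. At a 5% complication rate, the stated 5-point precision becomes 6.0 points with the permitted minimum of 50 patients and is met only at about 70. With no safety threshold set, the promise to determine safety is stronger than the data can support. Even zero complications leaves a two-sided upper limit of 7.1% (n=50) to 5.1% (n=70), results near the current rate in 50 patients leave a doubling open, and power against a doubling is 23% to 38%.

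This rests on reading the plus or minus 5% as percentage points, on two-sided 95% exact intervals, and on the approximate 5% in section 2 as the reference. It does not show that one-day discharge is unsafe, or that the study cannot usefully estimate complication rates.

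**What to change.** 1. **Section 5.1.** Restate the precision: for a rate of 5%, the 95% half-width is about 6 points with 50 patients and about 5 points with 70.
2. **Section 7.** Replace the promise to determine safety with a statement that the study will estimate the 30-day complication and readmission rates with exact 95% confidence intervals. This also brings the section into line with objective 2.
3. **Recommendations.** State that any safety recommendation will depend on the upper confidence limit, not on the observed rate being similar to the current 5%.

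The cost is wording only. No more patients or data are needed, and no clinical rule changes. The downside is a more modest stated conclusion.
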